**Table 3. Core and Site-specific IF Strategies**

Core IF activities (used across all facilitation teams)
Monthly site calls between external and internal facilitation teams
Monthly Community of Practice calls
Internal facilitation team engages EF team to support implementation
EF team engages internal facilitation team to support implementation
Academic Detailing/Education
Problem-solving based on assessment of implementation barriers and facilitators
Developing materials and adding them to a shared library
Informing local opinion leaders, leadership, and/or administrators
Site-specific IF activities
Audit and feedback (Specialty, Primary Care)
Site-specific learning collaborative (Acute Care)
Develop incentives (Primary Care)
Conduct cyclical, small tests of change (Primary Care)
Technical assistance (Primary Care)

facilitation teams will attend a monthly Community of Practice call. This has the distinct advantage of allowing internal facilitation teams across sites to learn about the full range of CONDUIT implementation activities. For example, if an internal facilitation team working the Specialty Care EF team is interested in moving beyond ORC and enhancing access to MOUD in the inpatient setting, they can learn from the Acute Care EF team. The Implementation Core will provide consultative expertise on the IF activities used by each facilitation team.

#### **D.4. Specific Aim 2: Evaluate Implementation Facilitation using a mixed methods approach to assess Reach, Effectiveness, Adoption, Implementation, and Maintenance.**

**D.4a. Overview:** The CONDUIT evaluation of IF will consist of two strategies: a mixed methods formative evaluation to gain site-level, granular understanding of implementation barriers and facilitators and guide IF tailoring, and quantitative outcomes evaluation guided by the RE-AIM framework.

**D.4b. Conceptual framework:** Two complementary frameworks will guide our evaluation of CONDUIT – the Consolidated Framework for Implementation Research (CFIR) and the RE-AIM framework, similar to previous work led by [name]. The CFIR will guide formative evaluation (**Table 4**). Within the RE-AIM framework, we will assess Reach, Effectiveness, Adoption, Implementation, and Maintenance as they apply to project work within each clinical setting (**Table 5**).

**D.4b. Formative evaluation:** A formative evaluation will be conducted at different stages of implementation and will assess Implementation and Maintenance outcomes (**Table 5**); see **Appendix 5** for a detailed timeline. For the developmental (pre-implementation) formative evaluations, the EF and internal facilitation teams and their staff will be responsible for collecting data related to facilitators and barriers and using rapid analysis techniques. They will be trained on rapid analytic techniques, requiring completion of templated matrices to identify key themes. If needed, an Implementation Core member will be available to attend calls and assist with completion of these evaluations and matrices. The EF team will conduct the developmental formative evaluation on a site-specific call during the pre-implementation period. The Implementation Core will develop a relatively brief semi-structured interview guide of the core CFIR constructs (**Table 4**), and

**Table 4.** Core CFIR Constructs Mapped to Implementation Facilitation Activities

Implementation Needs	CFIR Domain	CFIR Constructs	Implementation Facilitation (IF) Activities
Engagement of key clinical stakeholders	Intervention characteristics Inner setting	
 
▪ Adaptability
 
▪ Design quality & packaging
 
▪ Complexity
 
▪ Leadership engagement
 
▪ Tension for change
 
▪ Relative priority
 
	
 
▪ Academic detailing
 
▪ Informing local opinion leaders, leadership, administrators
 
▪ Problem-solving
 
▪ Regular contact with IF team
 
▪ Community of practice
 

Coordination of care across clinical settings	Inner setting	
 
▪ Networks and communications
 
▪ Ease of access to information/knowledge
 
	
 
▪ Developing materials (e.g., note templates) and adding them to a shared library
 
▪ Academic detailing
 
▪ Problem-solving
 

Providers believe engaging in MOUD is better than not engaging	Characteristics of individuals	
 
▪ Knowledge and beliefs about the intervention
 
▪ Self-efficacy
 
	
 
▪ Academic detailing
 
▪ Informing local opinion leaders, leadership, administrators
 

incorporate additional items based on unique needs of facilitation teams in differing clinical settings. Given the large and rapid scale of implementation, it is not feasible to conduct individual interviews of stakeholders, transcribe, and analyze the transcriptions.

For progress-focused formative evaluations, we will collect data in the monthly IF logs (**Appendix 6**), which is the same approach the larger SCOUTT initiative is using. It allows the facilitation teams and Implementation Core to track progress and address new barriers on monthly calls as they arise. The Implementation Core will provide monthly reports on the IF logs to each of the facilitation teams. For the interpretive evaluation, the Implementation Core will use stratified random sampling to select implementation sites for interviews post-maintenance. Approximately 3 to 5 sites per EF team (strata) will be selected randomly for in-person/phone interviews. We aim to interview key stakeholders, including Veterans, at 15 to 25 sites, with a target of approximately 5 participants per site, resulting in a final sample of 75 to 125 participants. We will use a CFIR-

guided semi-structured interview guide that will be designed to capture barriers, facilitators, and adaptations made to the original intervention and implementation activities. Although we plan to use audio recordings, they will not be transcribed given the rapid timeline of this project. We will use extensive notes and the recordings as needed to conduct a rapid analysis and pull illustrative quotes. Rapid analysis has been shown to produce equivalent findings to more resource-intensive, in-depth analytic techniques. The Implementation Core, in collaboration with the qualitative experts (e.g., Drs. [name] and [name]) across multiple settings, will conduct this evaluation.

**D.4c. Tracking IF activities and other implementation strategies:** The Implementation Core will rely on a standardized REDCap tracking log (see **Appendix 6** for sample tracking log) that EF and internal facilitation teams will complete monthly during the implementation phase, allowing for efficient data aggregation, cleaning, and analysis. See **Table 3** for core IF activities that will be captured across all sites as well as site-specific IF activities that will be captured in a modified REDCap tracking log that includes additional activities. The final format of these logs will be developed in partnership with the Quantitative/Economic Core so that they can be used to calculate return on investment in facilitation activities. The Quantitative/Economic Core will be responsible for aggregating and cleaning all data to be used for analyses related to implementation and cost, but in close partnership with the Implementation Core. If pre-implementation and implementation formative evaluation activities reveal barriers that require IF activities to be modified, then the REDCap tracking logs will be modified accordingly. For example, if an EF team is not using audit and feedback, but it is clear that a clinical setting does not perceive the need to change, they may add audit and feedback to their IF activities. We decided against using a more formal tailoring approach because those require more time and resources and our operational partners have a more rapid timeline in mind, although we can rely upon them should the partners prefer a more systematic approach.

Given that some site staff may rely on implementation strategies as part of local QI efforts that may fall outside of the IF activities measured in the logs, we will also ask internal facilitation teams to complete a web-based survey at baseline (pre-implementation) and then at the end of each study year. This survey captures a wide variety of implementation strategies beyond IF activities and has been used previously to evaluate implementation of a national initiative focused on engaging veterans with hepatitis C in treatment. The lead author, [name], part of the Implementation Core, will assist with adapting and analyzing the Expert Recommendations for Implementing Change (ERIC) survey for the needs of CONDUIT (see **Appendix 7** for sample survey). [name] and her team will summarize data from each site for the Implementation Core so that the latter can provide feedback to the EF teams about any implementation strategies to track monthly as part of IF activities. This data summary will include descriptive statistics about individual strategies and clusters of strategies used at the site over time. Correlational analyses will be conducted to assess the associations between strategies (individual strategies, number of strategies used, and clusters) and RE-AIM measures. This will allow us to understand which strategies are associated with improved site-level outcomes more broadly. Both the IF logs and the ERIC survey will allow us to assess Implementation outcomes (**Table 5**).

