**D.5. Specific Aim 3. Estimate the cost of implementation and return on investment**

**D.5a. Overview:** We use well-established methods with which our team has extensive experience to estimate the costs of implementation and return on investment with the primary goal of helping VISN leadership evaluate adoption, scale and spread of the clinical programs we implement.

**D.5b. Economic outcomes:** The primary economic outcome across all projects is cost per additional Veteran initiating MOUD. This includes both implementation costs and costs of delivering the clinical program/intervention. Return on investment will also be calculated and will include total costs including concurrent/downstream treatment and medical care costs.

**D.5c. External facilitation costs:** Cost and expenses associated with EF activities will be directly captured through monitoring of expenses associated with QUERI funding as well as VISN contributions. We anticipate that nearly 100% of support from QUERI will be allocated to implementation activities and tracked across the implementation efforts. Efforts that cannot be allocated individually to a specific clinical program (e.g. general interviews with national stakeholders) will be split equally across the relevant EF teams. Implementation staff will be asked to log collateral hours of effort they incur in excess of the QUERI and VISN support. Each month each investigator and project coordinator on the Implementation Core and each EF team will be asked to confirm that the effort allocated to the project (e.g. 10% FTE) and report how those hours were allocated to mutually exclusive implementation activities such as outreach/coordination with sites, planning, training, technical assistance, feedback, evaluation. This effort will be conducted in coordination with the VISN20 Tele-

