Pain PII (PI [name]), which is focusing on assessing the implementation costs associated with facilitation of expanding Tele-Pain to CBOCs in Alaska and Oregon. A recent effort by [name] of the QUERI partnered evaluation effort assessing implementation costs associated with the adoption of the Whole Health System of care utilized a similar strategy. A validation step in which implementation activities were re-reviewed with the guidance of a qualitative interviewer found this approach to be robust and reflective of actual implementation effort. Notably, some sites identified costs originally logged as implementation to be reclassified as care delivery activities or other non-related costs of the implementation effort. For this project, we will incorporate brief reviews with key personnel to help ensure appropriate attribution to implementation efforts.

**D.5d. Internal facilitation/site costs:** The Implementation and Quantitative/Economic Cores will rely on parallel efforts to assign costs to implementation efforts at each site, an approach we have refined in our experience with several large projects. In conjunction with the Implementation Core, we will develop items to be included in the monthly implementation log tracking using REDCap. These logs will be completed by sites' internal facilitators to collect data on personnel (e.g. time spent) and non-personnel costs (e.g. travel, supplies, equipment) associated with the implementation efforts. Additional semi-structured interview items capturing personnel time associated with any implementation burdens, as well as items for the 12-month post-implementation survey will also be developed based on the tracking logs and interviews.

**D.5e. Clinical program costs:** In order to identify specific delivery costs of each clinical program, we will utilize a micro-costing approach in which qualitative assessment of providers' time associated with the study is informed by time and motion studies. Process maps of each clinical activity will be generated for each of the five programs. [name] will train internal facilitators to perform time and motion studies as needed to identify estimates of typical times to complete specific program activities. [name] is currently leading the effort to calculate the cost of implementation for the national implementation of the SCOUTT initiative. Methods and tools developed for that evaluation will translate to this work.

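### The site effort log runs only in the implementation phase, so site teams' required pre-implementation hours have no prospective record and site implementation cost may be understated

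*Combined protocol and SAP*

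**What the plan says.** Four parts of the plan bear on this.

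- **When the log runs.** D.4c (Tracking IF activities) describes a standardized REDCap log "that EF and internal facilitation teams will complete monthly during the implementation phase". The same section says the logs will feed the return-on-investment calculation.
- **What the log is for on the cost side.** D.5d (Internal facilitation/site costs) has internal facilitators complete the monthly log "to collect data on personnel (e.g. time spent) and non-personnel costs (e.g. travel, supplies, equipment) associated with the implementation efforts". It adds a second source: "Additional semi-structured interview items capturing personnel time associated with any implementation burdens, as well as items for the 12-month post-implementation survey".
- **What site teams do beforehand.** D.4b (Formative evaluation) says of the developmental, pre-implementation stage that "the EF and internal facilitation teams and their staff will be responsible for collecting data related to facilitators and barriers". It continues: "They will be trained on rapid analytic techniques, requiring completion of templated matrices to identify key themes".
- **How external cost is captured.** D.5c says that external facilitation cost will be "directly captured through monitoring of expenses associated with QUERI funding as well as VISN contributions". Investigators and coordinators on the external teams and the Implementation Core also confirm their effort each month and split it across activities that include planning, training and evaluation.

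**The concern.** Site cost and external cost are measured over different windows. External effort is tracked from funding records and a monthly confirmation, neither of which is tied to a phase. Site effort is tracked mainly by a log that begins when implementation begins, although site staff have assigned duties before then.

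Aim 3 exists to help VISN leadership judge adoption, scale and spread, and its primary economic outcome is cost per additional Veteran started on MOUD. If site set-up hours are left out, the numerator of that ratio is too small, and both the ratio and the return on investment look better than they are. Hours not recorded at the time can later be recovered only by recall.

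**Working it through.** The plan states no figure for site hours, the length of pre-implementation, or the split between site and external cost, so there is nothing to reproduce. The check is a comparison of the sections, followed by algebra for direction and dilution.

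**Step 1. Is pre-implementation separate from the logged phase?** In the text supplied, yes. D.4b labels the developmental evaluation as pre-implementation. D.4c names pre-implementation and implementation evaluation activities separately and equates the baseline survey with pre-implementation. The implementation phase is not defined against each site's start date or the 3-month start-up period in D.4d1. Even if the log covers start-up, the developmental evaluation belongs to the earlier period.

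**Step 2. Who is recorded before implementation?**

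| Effort | Source | Stated window |
|---|---|---|
| External teams and Implementation Core | Funding and expense monitoring; monthly effort confirmation (D.5c) | No phase limit |
| Site teams, prospective | Monthly REDCap log (D.4c, D.5d) | Implementation phase |
| Site teams, retrospective | Interview items; 12-month post-implementation survey items (D.5d) | Period covered not stated |

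The monthly confirmation in D.5c does not include site staff. No prospective source of site hours exists for pre-implementation.

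**Step 3. Does the analysis correct for this?** D.5g obtains total facilitation cost by adding up the time and resource data that were collected. It states no adjustment for unlogged hours.

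**Step 4. Direction and dilution.** Let *S* be true site implementation cost, *E* external implementation cost, *D* program delivery cost, and *u* the share of *S* that falls before the log opens and is not recovered by interview or survey.

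- Proportional understatement of site cost: *u*
- Of implementation cost: *uS* / (*S* + *E*)
- Of the primary economic outcome, which D.5b says includes delivery cost: *uS* / (*S* + *E* + *D*)

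The count of additional Veterans started on MOUD comes from the Corporate Data Warehouse (Table 5), not the log, so the denominator of the cost ratio is unaffected. With *u* above 0, all three errors run toward lower cost. With *D* above 0, the third is smaller than the second. The documents give none of *u*, *S*, *E* or *D*, so the size cannot be calculated.

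**The case against.** The best defense is that the plan has other ways to reach this time. D.5d's interview and survey items on personnel time carry no phase limit, and D.5c ends with brief reviews with key personnel to check attribution. The log format is still to be developed, and D.5d itself ties the log to the implementation effort rather than to a phase. Appendix 5 (timeline), Appendix 6 (sample log) and the Gantt chart are not available here and might settle when the log opens. The work may also be modest: the external team runs the evaluation on a site call with a fairly brief guide, and there are no individual stakeholder interviews at that stage.

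Much of this stands, and it rules out several stronger readings that a reader might infer.

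- **That set-up time can never enter the cost.** The D.5d items could recover some of it.
- **That recovery is confined to the 15 to 25 sites sampled for post-maintenance interviews.** D.5d does not place its interview items in that sample, and it states no site sampling for the survey. The survey's absence from the D.4c survey schedule does not cancel it.
- **That the fidelity measure is also biased.** The pre-implementation work cited is not a listed facilitation activity in Table 3, which names problem-solving based on the assessment of barriers, not the assessment itself.
- **That a percentage can be put on the shortfall.** Any such figure would rest on assumed hours and cost shares.

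The defense does not supply a prospective record. The D.5d items are retrospective, are themselves to be developed from the logs and interviews, and are not said to reach back to pre-implementation. The D.5c reviews check how effort is attributed; they are not described as a way to collect unlogged hours. If the appendices do start the log earlier, D.4c still needs to agree with them.

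**Conclusion.** The concern holds in a limited form. Followed as written, the plan records external set-up effort as it occurs and leaves site set-up effort to possible later recall. Site implementation cost may be understated, and cost per additional Veteran started on MOUD and return on investment may look somewhat too favorable. The direction is clear if any site hours go unrecovered, but the size cannot be estimated from the documents. The proportional effect on the primary economic outcome is smaller than on implementation cost, because that outcome also carries delivery cost. Return on investment brings in downstream care costs as well.

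This rests on two assumptions: that D.4c's phase limit is meant literally, and that the material not shown does not open the log earlier. The point concerns Aim 3 only. It does not touch the Reach or Effectiveness outcomes. It is a cheap improvement to a stated data-collection rule.

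**What to change.** Amend D.4c and D.5d together:

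1. Open each site's REDCap log at the first pre-implementation contact and run it monthly through implementation.
2. Add a phase field (pre-implementation, start-up, implementation) and tie its values to the site start date and the 3-month start-up period in D.4d1.
3. Report cost per additional Veteran started on MOUD with and without pre-implementation cost, so that leaders can see the set-up component.
4. For sites already past that point, enter one back-dated record when the log opens, marked as recalled.
5. Check that Appendices 5 and 6 agree with the amended text.

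The cost is some plan wording, one field in an existing log, and a few extra entries per site by staff already assigned to complete it. The reported cost may become slightly less favorable. The back-dated entries will still depend on recall, but over a shorter interval than a 12-month post-implementation survey.

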Implementation of Opioid Use Disorder Treatment (or CONDUIT), to serve the dual purpose of expanding access to MOUD while examining effective IF activities that drive these outcomes. CONDUIT consists of 4 external facilitation (EF) teams partnering with internal facilitation teams at 57 sites across 6 VISNs to implement evidence-based practices across the OUD/pain continuum of care: Primary care, specialty care, acute care (hospital and emergency department) and telehealth (**Figure 1**). Three Cores – Veteran Engagement, Implementation, and Quantitative/Economic will work across teams and sites to ensure alignment of measures and to support cross-CONDUIT deliverables. Together, as a consortium, we will leverage our collective pilot work, resources and expertise to have the whole be greater than the sum of the parts.

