Each of the EF teams will work collaboratively with internal facilitation teams to deploy the core IF activities outlined in Table 3 as well as additional IF activities noted. Evaluations performed by the Implementation Core, in partnership with each facilitation team (e.g., formative evaluation, survey, IF logs as outlined in D4 below), will identify whether any adaptations need to be made to the IF activities. For example, if the Telehealth EF team identifies technical issues as a barrier to implementation, they will incorporate technical assistance into IF, and it will be added to their IF log for tracking its use during implementation.

**D.3d. Integration of implementation activities:** The foundation of CONDUIT's implementation activities are the structured interactions between the four EF teams and internal facilitation teams. A core set of IF activities will be used across all facilitation teams, and EF teams will use additional ones based on the needs of their sites or clinical settings (**Table 3**). EF and internal

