**D.4d3. Analytic approaches:** Our non-randomized evaluation design is necessary because randomization was not possible due to our partnership with VISN leadership and outreach efforts for individual site participation. A key goal is to demonstrate to VISN and facility leadership the value of implementation; therefore, we will estimate implementation outcomes for each of our individual sites and pool implementation sites as appropriate. This will allow us to provide descriptive quantitative information about individual implementation efforts to be combined with qualitative findings about implementation success. Although these analyses will allow for some comparison of effectiveness across individual team efforts, we do not propose formal direct comparisons of teams. There are several statistical limitations to the non-randomized evaluation design that we will address through pragmatic approaches. To account for secular trends in increased use of MOUD that may not be due to our implementation efforts, we will track other related implementation efforts such as initiation of additional SCOUTT efforts, and monitor national dashboards to generate a secular rate among non-intervention sites. We will use this secular rate and test to determine if CONDUIT activities increase use of MOUD above this rate, rather than a null hypothesis of 0. Because we are calculating outcomes for each of the individual sites, the risk of a spurious finding due to multiple testing is possible. We will use caution when interpreting any moderate p-values (e.g. 0.01 to 0.05) as significant. For ease in reporting to VISN and site leadership, we will utilize direct pre- and post-implementation period comparisons. Additional multivariate adjusted analysis using time-to-event semi-parametric methods will also be explored. These models will focus on initiation of MOUD treatment, and will allow for examining clinical and demographic characteristics, including time from initial OUD diagnosis.

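### The planned cross-site correlations of strategies with RE-AIM measures have no stated adjustment, so they mix a strategy's association with setting differences and with the barriers that prompted its use.

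*Combined protocol and SAP*

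**What the plan says.** Section D.4c, in the paragraph on the yearly web survey of implementation strategies (the ERIC survey), sets out the analysis: "Correlational analyses will be conducted to assess the associations between strategies (individual strategies, number of strategies used, and clusters) and RE-AIM measures". The stated use is: "This will allow us to understand which strategies are associated with improved site-level outcomes more broadly". No covariates, model or ordering in time are given. Section A describes one of the project's two purposes in stronger terms: "examining effective IF activities that drive these outcomes".

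Two other parts of the plan determine which sites use which activities.

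- **By setting.** Table 3 has eight core activities for all teams and five site-specific ones, each labelled with a setting. Incentives, small tests of change and technical assistance are listed for Primary Care; the learning collaborative for Acute Care; audit and feedback for Specialty and Primary Care. Section D.3d adds: "EF teams will use additional ones based on the needs of their sites or clinical settings".
- **By barrier.** Section D.4c gives the example of a team not yet using audit and feedback: if "it is clear that a clinical setting does not perceive the need to change, they may add audit and feedback to their IF activities". Section D.3b gives a similar example for Telehealth, where technical assistance would be added if technical problems are identified. The formative evaluation in D.4b describes monthly calls at which progress is followed and new barriers are dealt with.

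On comparisons between teams, D.4d3 says: "we do not propose formal direct comparisons of teams".

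**The concern.** A correlation across sites reads as information about the strategy only if the sites that use it are otherwise like those that do not. Here they differ for two reasons built into the design. Where an activity belongs to one setting, users and non-users are different settings served by different EF teams, and the coefficient carries whatever else separates those settings. Where an activity is added because a barrier was found, users are sites with more obstacles, and the coefficient carries the effect of those obstacles too. The first can push the coefficient either way. The second would usually push it down, so that a useful strategy could look useless or harmful.

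At stake is the interpretation of which strategies go with better site outcomes. The overall estimate of whether implementation worked is not affected.

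**Working it through.** **The plan's own figure.** There is none for this analysis. Table 6 counts at-risk Veterans, not sites. It is reproduced by d = (1.960 + 0.842)/√n, with two-sided alpha 0.05 assumed: 0.396, 0.323, 0.198 and 0.102 for n = 50, 75, 200 and 750, against the stated 0.40, 0.32, 0.20 and 0.10. It says nothing about the strategy correlations.

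**Step 1: what Table 3 leaves once setting is known.** EF teams are named by setting, so the two are treated as one factor with four levels. Assume every site uses exactly the activities listed for its setting. Then:

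- incentives = small tests of change = technical assistance = Primary Care indicator;
- learning collaborative = Acute Care indicator;
- audit and feedback = Primary Care + Specialty indicators;
- each core activity, coded used or not used, is constant.

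The four setting indicators have rank 4. Adding the five site-specific activities leaves the rank at 4, and adding the eight core activities still leaves it at 4. As listed, the activities carry no information beyond setting. Only departures from the list, or differences in frequency and duration, can add any.

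**Step 2: size of the setting effect.** Inputs: 57 sites (D.3c; the Table 2 rows sum to 24 + 33 = 57, although D.2 mentions 64). Assumptions: 14 sites in one setting, a strategy used only there with no effect, and a setting gap of d SD in outcome level.

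r = d / √(d² + 1/(p(1 − p))), with p = 14/57 = 0.2456, so 1/(p(1 − p)) = 5.397.

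- d = 0.5: r = 0.5/√(0.25 + 5.397) = 0.210; t on 55 df = 1.60, p = 0.116.
- d = 1.0: r = 1/√(1 + 5.397) = 0.395; t = 3.19, p = 0.0023.

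A simulation of 10,000 runs, with 15 of 57 sites in the setting, gave mean r of 0.11, 0.22, 0.32 and 0.41 at gaps of 0.25, 0.5, 0.75 and 1 SD. The null strategy reached p < 0.05 in 13%, 38%, 69% and 91% of runs.

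These figures are for outcome levels. If change from the pre-implementation value is used, a gap that is stable over time cancels, and d becomes the difference between settings in mean change.

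**Step 3: size of the barrier effect.** Assumptions: 57 sites; a standardised barrier score B; log-odds of adding the activity = kB; outcome = b × activity − gB + noise with total SD of about 1. Mean difference between users and non-users, in SD:

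| g | k | no true effect (b = 0) | true benefit (b = 0.5) |
|---|---|---|---|
| 0.3 | 1 | −0.25 | +0.25 |
| 0.3 | 2 | −0.36 | +0.14 |
| 0.5 | 1 | −0.41 | +0.08 |
| 0.5 | 2 | −0.61 | −0.11 |
| 0.7 | 1 | −0.58 | −0.08 |
| 0.7 | 2 | −0.85 | −0.35 |

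With k = 0 (no reactive addition) the 0.5 SD benefit is recovered (0.49 to 0.50). The documents give neither g nor k.

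**Step 4: does another analysis repair this?** Each site as its own control (D.4d1), the secular rate (D.4d3) and the mixed models (D.5g) address implementation as a whole. D.5g mentions levels of facilitation, but the exposure terms it names are implementation and program status and the interaction with time. None has strategy as the exposure.

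**Step 5: precision.** Detectable correlation at 80% power = tanh(2.802/√(n − 3)): 0.36 for 57 independent sites, 0.50 if the 29 health care systems in Table 2 are the units, and 0.69 within a setting of 14 sites. For a partial correlation with four covariate terms (three for setting, one for baseline) across 57 sites: tanh(2.802/√50) = 0.38.

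**The case against.** The strongest reply is that the correlation sentence belongs to the ERIC survey, which exists to capture strategies outside the logged IF activities. Nothing shows that those strategies are allotted by setting, so the rank result and the activity counts from Table 3 (12 for Primary Care, 9 for Specialty, 9 for Acute Care, 8 for Telehealth) are not shown to describe the survey variables. This stands. It limits the setting argument to IF activities, but leaves the concern about use in response to barriers.

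Also fair:

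- Table 3 calls the extra activities site-specific and D.3d ties them to sites or settings, so use may vary within a setting. Reactive additions themselves create such variation. The rank result is therefore a limiting case.
- D.4c promises only association. The causal wording comes from section A, and D.4d3 acknowledges the limits of a non-randomized design and combines the numbers with qualitative findings.
- D.4c speaks of improved outcomes. If that means change scores, stable setting differences drop out.

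A reader might go further and infer three things that the documents do not support. One is that strategies are added where measured progress is poor: the text says barriers, some found before implementation. Another is that these correlations will shape the toolkit: G.2 describes refining the Phase 1 toolkits, and what D.4c feeds back to EF teams is a descriptive summary. The third is that no analysis could be informative: dated additions and the amount of each activity can vary within a setting. None of these replies supplies the missing adjustment.

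**Conclusion.** The concern holds for the analysis as written. For IF activities, a raw cross-site correlation combines the strategy's association with setting differences and with the barriers that led to its use, and no other model in the plan separates them. For survey strategies beyond Table 3, the link to setting is possible but unproven; the barrier problem remains.

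The size is conditional. With outcome levels and 14 of 57 sites in one setting, a null strategy confined to it shows r of about 0.21 at a 0.5 SD gap and 0.40 at 1 SD; the split and the gap are both assumed. The barrier results depend on an assumed strength of reactive use. It would be too strong to say that the plan claims causal findings from this analysis, or that its main evaluation is compromised. This is a cheap improvement to a secondary analysis, and worth making.

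**What to change.** In D.4c, replace the raw correlation with the following.

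1. Model the change in each site's outcome from its pre-implementation value on the strategy measure, with terms for EF team/setting and for the site's pre-implementation MOUD rate.
2. As a sensitivity analysis, where dates allow (monthly logs, baseline and annual survey waves), use strategy measured before the outcome interval.
3. Report activities used at all sites, or only at sites of one setting, descriptively and without ranking.
4. Label the results exploratory associations, not evidence of which activities drive outcomes.

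The cost is SAP wording and modest analysis, since the logs, survey and Corporate Data Warehouse outcomes are already planned. Intervals will be wider, and activities confined to one setting will have little or no estimate, which the raw correlation could not validly give either. Confounding by barriers is reduced but not removed, because the pre-implementation rate is only a partial stand-in for barriers.

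A quarterly lagged analysis within each setting as the main method is a debatable trade-off. Counts at small clinics may be very low (three CBOCs together reached 12 patients in Phase 1), and about 14 sites could detect only r near 0.69. It is not needed to meet this point.
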